10.5 Vaccine Accountability and Storage

The Investigator and study staff will be responsible for the accountability of all study vaccines (dispensing, inventory and record keeping) and adherence to GCP guidelines as well as appropriate regulations. Study vaccines will be stored according to the instructions on the label as received by the manufacturer.

The Investigator will not allow the study vaccine to be used other than as directed by this protocol. Study vaccines will not be dispensed to any individual who is not randomised in the study.

An accurate and timely record of the receipt of all study vaccines, dispensing to volunteers, collection of unused study vaccines returned, and subsequent return of unused study vaccines to the Sponsor (or designated distributor) must be maintained. This includes, but may not be limited to, receipt of study vaccines, IMP accountability logs, IMP return documentation and shipping receipts.

The supplies and inventory records must be made available, upon request, for inspection by the designated representative of the Sponsor or a representative of a regulatory authority. All unused study vaccines will be reconciled and handled in agreement with the Sponsor.

The Investigator must ensure the availability of an appropriate storage location and the recording and evaluation of storage conditions. The responsible pharmacist will keep an inventory. This will include a description of the formulation and the quantity of investigational materials received for the study and a record of the materials that are dispensed, to whom and when.

Upon termination of the study the pharmacist will conduct a final inventory of the medication supply and will record the results of this inventory in the Drug Accountability Form. Unused medication will be returned to the Sponsor (or designated distributor) or destroyed at the end of the study according to instructions provided by the Sponsor.

11. PRIOR AND CONCOMITANT MEDICATION, AND OTHER RESTRICTIONS

11.1 Prior Medications

Medications which are not permitted prior to study start are detailed in the exclusion criteria.

11.2 Concomitant Medications

Chronic medications such as antihypertensives, bronchodilators, oral contraceptives or statins that do not affect the immune system, will be permitted and allowed to continue during the study at the discretion of the Investigator. Paracetamol will be permitted for the treatment of headache or other symptoms.

Any medication the volunteer takes other than study vaccine, including herbal and other non-traditional remedies, is considered a concomitant medication. All concomitant medications taken during the study must be recorded in the CRF.

11.3 Other Restrictions

The Investigator or designee will request that volunteers abstain from:

- Donation of blood or blood products for 90 days after the last dose of trial medication.
- Consumption of alcoholic beverages within 24 hours prior to dosing.
- Use of cosmetics or creams at the site of vaccination within 24 hours prior to dosing.
- Excessive exercise or a significant change in usual exercise habit within 7 days prior to dosing and for 7 days post dosing.

12. STUDY CONDUCT

12.1 Screening Period (Part A and Part B)

Screening assessments for Part A and Part B will be performed within 28 days prior to the first study vaccine administration (Day 1). The following assessments will be carried out at the screening visit (Visit 1) after written informed consent has been obtained:

- Inclusion/Exclusion
- Demography
- Medical history
- Physical examination
- Height, weight, body mass index (BMI)
- Vital signs (heart rate, blood pressure, tympanic temperature and respiration rate)
- 12-lead electrocardiogram (ECG)
- Urinalysis
- Blood samples for haematology and biochemistry
- Blood samples for HIV, hepatitis B and hepatitis C
- Serum pregnancy test for females of child-bearing potential
- Alcohol breath test
- Urine drugs of abuse test (methadone, methamphetamine, cannabis, phencyclidine, benzodiazepines, cocaine, opiates, tricyclic antidepressants, barbiturates and amphetamines)
- A review of all medications taken in the previous month

12.2 Treatment Period and Post-Study Period

12.2.1 Part A

Volunteers will receive one of up to 7 dosing regimens of GBS-NN or placebo on 1 or 2 occasions – a primary dose will be administered at Visit 2 and volunteers will remain in the study unit for at least 8 hours post-dose, and if a booster dose is required, this will be administered at Visit 6. There will be a time interval of 4 weeks between Visit 2 and Visit 6, although this time interval may change if the dosing regimen is changed. There will be 10 volunteers in each group, 8 randomised to active and 2 to placebo. All cohorts in Part A will incorporate sentinel dosing of 2 volunteers in each cohort for the primary dose only: 1 on active treatment and 1 on placebo. No further volunteers in that cohort will be dosed until at least 24 hours after dosing the second volunteer, provided that there are no serious or unexplained safety issues as determined by the Investigator.

The decision to proceed with administration of the primary dose in subsequent cohorts will be made as described in Section 12.5.

The following assessments will be carried out at these visits:

Visit 2

A urine pregnancy test, brief physical examination, urine drugs of abuse test and alcohol breath test will be performed to confirm eligibility. Eligible volunteers will be randomised to receive active or placebo on 1 or 2 occasions (all volunteers will receive a primary dose at Visit 2 and a booster dose of the same medication (active or placebo) will be administered at Visit 6 if required). The dose administered, the number of doses and the time interval between doses will be dependent on the data generated from the preceding cohort and will be decided by the Safety Review Committee. A pharmacodynamic blood sample will be taken to measure pre-existing antibody levels prior to dosing. The primary dose will be administered at Visit 2 and volunteers will remain in the study unit for at least 8 hours post-dose. Vital signs will be recorded pre-dose and at 2 and 6 hours post-dose. A brief medical examination (including an assessment of the injection site) will be performed prior to discharge to ensure the volunteer is fit for discharge.

Visit 3

Visit 3 will be performed 24 hours (\pm 2 hours) after administration of the primary dose and an assessment of the injection site will be performed, vital signs will be recorded and AEs and concomitant medications will be reviewed.

Visit 4

Visit 4 will be performed 1 week after administration of the primary dose. An assessment of the injection site will be performed, vital signs will be recorded, safety blood samples for haematology and biochemistry will be collected, urinalysis will be performed and AEs and concomitant medications will be reviewed.

Visit 5

Visit 5 will be performed 2 weeks after administration of the primary dose. This visit will be performed via telephone and a review of AEs and concomitant medications will be performed.

Visit 6

Visit 6 will be performed 4 weeks after Visit 2. A booster dose will or will not be administered at this visit depending on the decision made by the Safety Review Committee for each cohort.

If a booster dose is administered at this visit, the following assessments will be performed: an assessment of the injection site and a pharmacodynamic blood sample will be taken to measure antibody response prior to dosing. A urine pregnancy test will be performed prior to dosing. A booster dose will be administered. Volunteers will remain in the study unit for at least 4 hours post-dose. Vital signs will be recorded pre-dose and at 2 hours post-dose. A brief medical examination (including an assessment of the injection sites) will be performed prior to discharge to ensure the volunteer is fit for discharge.

If a booster dose is not administered at this visit, the following assessments will be performed: an assessment of the injection site and a pharmacodynamic blood sample will be taken to measure antibody response.

AEs and concomitant medications will be reviewed whether a booster dose is administered or not.

Visit 7 (Only if a booster dose is administered)

Visit 7 will be performed 24 hours (\pm 2 hours) after administration of the booster dose and an assessment of the injection sites will be performed, vital signs will be recorded and AEs and concomitant medications will be reviewed. If a booster dose is not administered, this visit will not be performed.

Visit 8

Visit 8 will be performed 2 weeks following Visit 6 and the following assessments will be performed: an assessment of the injection sites, vital signs will be recorded, safety blood samples for haematology and biochemistry will be collected, urinalysis will be performed, a pharmacodynamic blood sample will be taken to measure antibody response and AEs and concomitant medications will be reviewed.

Visit 9

Visit 9 will be performed 8 weeks following the first study vaccine administration and the following assessments will be performed: an assessment of the injection site and a pharmacodynamic blood sample will be taken to measure antibody response and AEs and concomitant medications will be reviewed.

Post-Study Medical (Visit 10)

A post-study medical will be performed 12 weeks following the first study vaccine administration and the following assessments will be carried out: an assessment of the injection site, a pharmacodynamic blood sample will be taken to measure antibody response, physical examination, vital signs, 12-lead ECG, urinalysis, blood samples for haematology and biochemistry, serum pregnancy test (if applicable) and a review of AEs and concomitant medications.

Safety Follow-Up (Visit 11)

A safety follow-up phone call will be performed 3 months after the end of the study (Visit 10) i.e. 6 months following the first study vaccine administration to check the general health of the volunteer and to review significant AEs.

[REDACTED]

In both Part A and Part B, following the primary dose volunteers will remain in the study unit for 8 hours post-dose to ensure that no significant AEs occur and the medicinal product is well tolerated. No additional acute safety concerns are considered likely to occur following 8 hours of observation. Following the booster dose volunteers will remain

in the clinic for at least 4 hours post-dose, as the volunteer has tolerated the initial dose, and therefore, tolerability should be consistent. The concern is for an acute systemic reaction following the booster dose. It is not considered necessary to keep the volunteers in the study unit overnight as no samples are being taken and the time intervals are considered appropriate to assess the safety and tolerability prior to discharge.

12.2.2 Part B

Volunteers will receive one of 3 dosing regimens (X, Y or Z) of GBS-NN or placebo on 1 or 2 occasions – a primary dose will be administered at Visit 2, and if a booster dose is required, this will be administered at Visit 6. There will be up to 80 volunteers in each group, up to 60 randomised to active vaccine and up to 20 to placebo.

The following assessments will be carried out at the visits during the Treatment Period:

Visit 2

A urine pregnancy test, brief physical examination, urine drugs of abuse test and alcohol breath test will be performed to confirm eligibility. Eligible volunteers will be randomised to receive active or placebo on 1 or 2 occasions (all volunteers will receive a primary dose at Visit 2 and a booster dose will be administered at Visit 6 if required). The dose administered and the number of doses will be decided based on the results of Part A. Vaginal and rectal swabs will be taken to assess colonisation by Group B streptococcus (GBS) and a pharmacodynamic blood sample will be taken to measure pre-existing antibody levels prior to dosing.

The primary dose will be administered at Visit 2 and volunteers will remain in the study unit for at least 2 hours post-dose. Vital signs will be recorded pre-dose and at 2 hours post-dose. A brief medical examination (including an assessment of the injection site) will be performed prior to discharge to ensure the volunteer is fit for discharge.

Visit 3

Visit 3 will be performed 24 hours (\pm 2 hours) after administration of the primary dose and an assessment of the injection site will be performed, and vital signs will be recorded and AEs and concomitant medications will be reviewed.

Visit 4

Visit 4 will be performed 1 week after administration of the primary dose by telephone to review AEs and concomitant medications.

Visit 5

Visit 5 will be performed 2 weeks after administration of the primary dose and the following assessments will be performed: an assessment of the injection site, and AEs and concomitant medications will be reviewed, a pharmacodynamic blood sample will be taken to measure antibody response. Vital signs will be recorded, safety blood samples for haematology and biochemistry will be collected and urinalysis will be performed.

Visit 6

Visit 6 will be performed 4 weeks after Visit 2, although this time interval may change depending on the dose regime chosen. A booster dose will or will not be administered at this visit depending on the dose regime chosen.

If a booster dose is administered at this visit, the following assessments will be performed: an assessment of the injection site, vaginal and rectal swabs will be taken to assess colonisation by GBS and a pharmacodynamic blood sample will be taken to measure

antibody response prior to dosing. A urine pregnancy test will be performed prior to dosing. A booster dose will be administered. Volunteers will remain in the study unit for at least 2 hours post-dose. Vital signs will be recorded pre-dose and at 2 hours post-dose. A brief medical examination (including an assessment of the injection sites) will be performed prior to discharge to ensure the volunteer is fit for discharge.

If a booster dose is not administered at this visit, the following assessments will be performed: an assessment of the injection site, vaginal and rectal swabs will be taken to assess colonisation by GBS and a pharmacodynamic blood sample will be taken to measure antibody response.

AEs and concomitant medications will be reviewed whether a booster vaccination is administered or not.

Visit 7 (To be conducted only if a booster dose is administered)

Visit 7 will be performed 24 hours (\pm 2 hours) after administration of the booster dose and an assessment of the injection sites will be performed, vital signs will be recorded and AEs and concomitant medications will be reviewed. If a booster dose is not administered, this visit will not be performed.

Visit 8

Visit 8 will be performed 2 weeks after Visit 6 and the following assessments will be performed: an assessment of the injection sites, vital signs will be recorded, safety blood samples for haematology and biochemistry will be collected, urinalysis will be performed, a pharmacodynamic blood sample will be taken to measure antibody response and AEs and concomitant medications will be reviewed.

Visits 9 and 10

These are follow-up visits for the assessment of pharmacodynamic markers and/or safety up to the timing of the primary endpoint (Visit 10 i.e. Week 12).

Visit 9 (week 8) and Visit 10 (week 12, timing of primary endpoint) will take place at the study unit and the following assessments will be performed: vaginal and rectal swabs will be taken to assess colonisation by GBS, a pharmacodynamic blood sample will be taken to measure antibody response, vital signs will be recorded, an assessment of the injection sites will be performed and AEs and concomitant medications will be reviewed. At Visit 10 (week 12) a urine pregnancy test will also be performed.

Visits 11, 12, 13, 14, 15, 16, 17, 18 and 19

Visit 11 (week 16), Visit 13 (week 24), Visit 15 (week 32) and Visit 17 (week 40) will take place at the study unit and the following assessments will be performed: vaginal and rectal swabs will be taken to assess colonisation by GBS, a pharmacodynamic blood sample will be taken to measure antibody response, vital signs will be recorded, an assessment of the injection site will be performed and significant AEs and concomitant medications will be reviewed.

The remaining visits [Visit 12 (week 20), Visit 14 (week 28), Visit 16 (week 36), Visit 18 (week 44) and Visit 19 (week 48)] will be conducted via a phone call and AE's and concomitant medications will be reviewed.

Post-Study Medical (Visit 20)

A post-study medical will be performed 12 months following the first injection and the following assessments will be carried out: an assessment of the injection site, vaginal and rectal swabs will be taken to assess colonisation, a pharmacodynamic blood sample will

be taken to measure antibody response, physical examination, vital signs (heart rate and blood pressure, including tympanic temperature and respiration rate), 12-lead electrocardiogram (ECG), urinalysis, blood samples for haematology and biochemistry, serum pregnancy test (if applicable) and a review of AEs and concomitant medications.

[REDACTED]

Phenotypic and genetic analyses may be performed on GBS strains isolated from volunteers' vaginal and rectal swabs.

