The normal adverse event profiles from Phase I studies suggest that a typical array of minor clinical study symptoms may be experienced by volunteers taking part in the study. GBS-NN has not previously been tested in human volunteers, although it is known that naturally occurring antibodies, reactive against the GBS-NN are found in pregnant women; the possibility of as yet unknown side effects should remain a consideration. The protocol requires that volunteers are monitored after vaccine administration (vital signs and general signs and symptoms), with regular follow-up visits for physician assessment and questioning regarding AEs will be conducted for all volunteers in the study. GBS-NN, like other protein-based vaccines, may theoretically be associated with a transient febrile reaction (body temperature greater than 38.0°C but not greater than 38.7°C) following vaccination. Immune complex-mediated reactions are unlikely given the recombinant nature of GBS-NN, however, it is still possible that hypersensitivity may occur.

Based on the results from clinical use of other protein vaccines adsorbed to Alhydrogel®, and other aluminium containing adjuvants transient local reactions at the injection site, including pain, oedema, bruising, erythema and induration, mainly of mild intensity, are likely to occur. In addition flu-like symptoms, such as fatigue, malaise, myalgia, and mild to moderate headache may occur.

GBS-NN vaccination is contraindicated in volunteers known to suffer hypersensitivity reactions to vaccines or a known allergy to aluminium hydroxide. For the purpose of the study volunteers who have experienced a significant illness in the four weeks prior to check in will be excluded. The vaccine should not be given to volunteers with known or suspected immune deficiency, autoimmune diseases or who have an acute infection.

GBS-NN should not currently be given to women known, or suspected to be, pregnant, or to nursing mothers. Currently GBS-NN should only be administered to women of child-bearing potential if adequate contraceptive precautions are taken, accompanied by serum and/or urine pregnancy testing prior to vaccination and during follow up.

All study volunteers will be monitored for potential side effects of vaccination during the entire course of the study, as per the protocol, and adverse events must be appropriately followed up.

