7. STUDY OBJECTIVES AND ENDPOINTS

7.1 Primary Objective

The primary objective is to evaluate the safety and tolerability of the GBS-NN vaccine for 12 weeks after the first dose of vaccine.

The following endpoints will be evaluated to support this objective: local and systemic reactogenicity; adverse events; laboratory tests; urinalysis; vital signs; 12-Lead ECG parameters; physical examination.

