14. ADVERSE EVENTS, SERIOUS ADVERSE EVENTS AND REPORTING

14.1 Adverse Events (AEs)

An AE is any untoward medical occurrence in a volunteer to whom a medicinal product has been administered, including occurrences which are not necessarily caused by or related to that product.

An AE can be:

- Any unfavourable and unintended sign (including reactions from overdose, abuse, incorrect use of any treatment, or interaction)
- Any new disease or exacerbation of an existing disease (e.g. increase in frequency or worsening in nature)
- Any deterioration in measurements of laboratory values or other clinical tests (e.g. ECG, vital signs or X-ray) that results in symptoms, a change in treatment, or discontinuation from the IMP
- Recurrence of an intermittent medical condition (e.g. headache) not present at baseline
- Other medical events regardless of their relationship to the IMP, such as accidents, falls and any injuries resulting from them.

AEs will be recorded from the start of the study, i.e. from the first visit to the study unit on Day 1, until the post-study medical visit.

After completion of the 12 week period following the first vaccination in Part B (i.e. after Visit 10), AEs will be recorded by the volunteer in a diary card, and only those deemed to be relevant or significant by the Investigator will be recorded in the eCRF. A relevant or significant AE will be any event that caused the patient to visit any health care professional. These events will be recorded and the Investigator will determine if the event was possibly related to the investigational product. Any event deemed serious will be processed as a SAE in the normal way and if considered related reported as a SUSAR.

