15.4.2 Primary endpoint for the two study parts

The primary objective is to evaluate the safety and tolerability of the GBS-NN vaccine for 12 weeks after the first dose of vaccine.

All the included volunteers (including the withdrawal and dropout volunteers) will be evaluated for safety analysis (ITT).

The following endpoints will be evaluated:

- **Local and systemic reactogenicity**

Assessment results will be described according to treatment/dose group and visit.

- **Adverse events**

Adverse events will be coded according to the Medical Dictionary for Regulatory Activity (MedDRA). They will be classified into pre-defined standard categories according to chronological criteria:

- Treatment Emergent Adverse Events (TEAEs): AEs which occur for the first time after the first administration or present before and worsened during vaccine exposure;
- Non-Treatment Emergent Adverse Events (NTEAEs): AEs which occur before the first study vaccine administration (also called "pre-dose event").

TEAEs will be described by relation to study vaccine (for example: definite / probable / possible / unlikely / unrelated) and maximum intensity (for example: mild / moderate / severe) according to treatment/dose group. Descriptive statistics will be characterised by number of TEAEs, number and percentage of volunteers with at least one TEAE (based on ITT). In case of few TEAEs (≤ 5 per study part for example), only a listing will be performed.

Vaccine related TEAEs (*i.e.* definite, probable or possible relationship to study vaccine) will be summarised by MedDRA codes (SOC and PT) and treatment/dose group. In case of few vaccine related TEAEs (≤ 5 per study part for example), only a listing will be performed. TEAEs not related to study vaccine (*i.e.* unlikely or unrelated relationship to study vaccine) will also be summarized by MedDRA codes.

Two distinct listings of TEAEs and NTEAEs will be presented by treatment/dose group, volunteer and MedDRA codes in order to provide more information about adverse events (example: description, duration, time since last administration if applicable, seriousness, any actions taken as concomitant medication or hospitalization).

- **Laboratory tests**

Biochemistry and haematology tests will be performed at V1 (screening), V4 (part A), V5 (part B), V8 (parts A and B) and post-study medical visit (V10 for part A and V20 for part B).

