Volunteers will be asked if they experience any pain. If the answer is yes, they will be asked to rate the level of pain on a scale of 1-10. Assessment of pain will commence after first injection.

Any other local reaction (for example: necrosis or ulceration)? Please specify

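### After both Part B doses and the Part A booster, the injection site is not graded for 13 days after the 24-hour check, so short-lived reactions in that interval stay outside the graded primary endpoint

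*Combined protocol and SAP*

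**What the plan says.** Section 7.1 lists the primary endpoints as "local and systemic reactogenicity; adverse events; laboratory tests; urinalysis; vital signs; 12-Lead ECG parameters; physical examination". Section 6.3 expects "transient local reactions at the injection site, including pain, oedema, bruising, erythema and induration".

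**Part B, dose 1 (Section 12.2.2).** On Day 1, "A brief medical examination (including an assessment of the injection site) will be performed prior to discharge", at least 2 hours after the dose. Visit 3, timed at 24 hours with a window of ±2 hours, falls "after administration of the primary dose and an assessment of the injection site will be performed, and vital signs will be recorded". The Day 8 contact is a telephone call: "Visit 4 will be performed 1 week after administration of the primary dose by telephone to review AEs and concomitant medications". The site is next assessed at Visit 5, Day 15.

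**Booster, both parts (Sections 12.2.1 and 12.2.2).** The site is assessed before discharge, at Visit 7 (24 hours after the booster) and at Visit 8 (2 weeks after Visit 6). No contact is scheduled between Visits 7 and 8. Part A dose 1 differs: its Day 8 visit is in person and includes the injection site.

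**Grading and reporting.** Under Appendix 1, clinical staff grade redness and bruising by size, and induration by palpation and size. Itching is present or absent. For pain, "Volunteers will be asked if they experience any pain", with a 1–10 rating if the answer is yes. Section 15.4.2 says of local and systemic reactogenicity: "Assessment results will be described according to treatment/dose group and visit". Section 15.1.3 commits to comparing intensity scores between vaccine dose groups. Section 15.1.1 restricts post-vaccination values to scheduled assessments.

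**Other capture.** Until Day 85, volunteers report adverse events spontaneously (Section 14.3) and are asked about them at scheduled contacts. Only in Part B, and only after Visit 10, does Section 14.1 say that "AEs will be recorded by the volunteer in a diary card".

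**The concern.** The protocol expects local reactions that come and go. For three of the four doses, the graded observations fall in the first day and then at two weeks, so the rest of the first week is not graded. The Part B schedule marks the site again at Days 57, 85, 113, 169, 225, 281 and 365, by which time a transient reaction would be over.

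Appendix 1, as legible, describes the state at the time of assessment and has no item for the worst reaction since the last contact. An unscheduled check is possible at the investigator's discretion (Section 12.3), but Section 15.1.1 would leave its result out of the summaries.

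What is at stake is the ability of a primary endpoint to show how often local reactions occur and how strong they become on the Appendix 1 scale, and so the sensitivity of the planned comparison of intensity between dose groups. The individual criterion for a severe injection-site reaction in Section 12.6 also refers to Appendix 1, so it draws on the same observations.

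**Working it through.** The plan states no figure to reproduce. The check counts days between consecutive injection-site assessments, using the visit text in Section 12.2, both Schedules of Assessments in Section 18 and the windows in Section 12.4.

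**Step 1: nominal gaps.** The discharge assessment comes first for every dose: at least 8 hours after Part A dose 1, at least 4 hours after the Part A booster, and at least 2 hours after either Part B dose.

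| Dose | Later assessments, days after dose | Gap after the 24-hour check |
|---|---|---|
| Part A dose 1 | 1, 7, 28 | 8 − 2 = 6 days |
| Part A booster | 1, 14, 28 | 43 − 30 = 13 days |
| Part B dose 1 | 1, 14, 28 | 15 − 2 = 13 days |
| Part B booster | 1, 14, 28 | 43 − 30 = 13 days |

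The booster is conditional and its interval may change. Visit 8 stays 2 weeks after Visit 6, so the 13 days do not change.

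**Step 2: windows.** Visits 3 and 7 have ±2 hours; Visits 5 and 8 have ±1 day.
- Shortest gap: 13 − 1 − 2/24 = 11.9 days.
- Longest gap: 13 + 1 + 2/24 = 14.1 days.

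For a volunteer seen within the windows, nothing between 26 hours and 14 − 1 = 13 days after the dose is graded at a scheduled assessment.

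**Step 3: contacts inside the gap.** In Part B after dose 1, the call falls 8 − 2 = 6 days after Visit 3 and 15 − 8 = 7 days before Visit 5. It reviews adverse events and medications, and the schedule has no injection-site mark for it. After the booster there is no contact in either part.

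**Step 4: illustration on assumed onset and duration.** The documents give neither. Suppose onset is uniform over the first W days after the dose and each reaction lasts L days, with L from 1 to 7. For either Part B dose and the Part A booster, a reaction is present at the 24-hour check if it began within the first day, which has probability 1/W. With W up to 3 it has ended by 3 + 7 = 10 days, so the two-week visit adds nothing. The share present at any grading is then:
- W = 1: 1/1 = 100%
- W = 2: 1/2 = 50%
- W = 3: 1/3 = 33%

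A simulation with W = 3 gave 33% at each duration tried (1, 2, 3, 5 and 7 days). For Part A dose 1, with its Day 8 visit, it gave 33% at 1 to 3 days, 67% at 5 days and 100% at 7 days. Daily grading on days 0 to 7 gave 100%. These figures show how the result depends on onset. They are not estimates for this vaccine.

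**The case against.** The strongest reply is that safety capture does not stop between gradings. Adverse events are reviewed for every volunteer at each scheduled contact, including the Part B Day 8 call, and volunteers are told to report events as soon as possible. Adverse events are themselves a primary endpoint. They carry a mild, moderate or severe intensity (Section 14.2.1), and Section 15.4.2 tabulates treatment-emergent events by maximum intensity and by number and percentage of volunteers. A reader might infer that the endpoint shrinks to a snapshot at 24 hours, or that adverse events are solicited unevenly. The documents support neither reading. What remains is that this intensity scale is functional, whereas Appendix 1 grades redness, bruising and induration by size or palpation. An adverse event record therefore does not supply the missing grade.

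A reader might also infer that Part A dose 1 cannot be compared fairly with dose 2 or with Part B. The two parts are reported separately (Section 15.1.1), and the planned reactogenicity test is between vaccine dose groups. Within a part, active and placebo follow the same schedule under blinding. The gap lowers sensitivity; it does not by itself bias those contrasts.

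Finally, Section 15 leaves detail to a statistical analysis plan. The eCRF is not available, and Appendix 1 includes figures not shown, so a field for the worst reaction could exist. That limits what can be said about recording. It does not alter the visit schedule, on which the text and both tables agree.

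**Conclusion.** The point holds for three of the four doses: Part B dose 1, the Part B booster and the Part A booster. Each has 13 days without a scheduled grading after the 24-hour check (11.9 to 14.1 with windows), against 6 days after Part A dose 1. Following the plan exactly, a local reaction confined to that interval receives no Appendix 1 grade, and one that peaks there is seen only below its peak. It enters neither the by-visit summary nor the intensity comparison at its true strength.

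The loss is in the graded endpoint and in the sensitivity of the comparison between dose groups. It is not a loss of all safety information, and the primary endpoint can still be collected. No percentage of reactions affected can be drawn from the documents; the range in the working depends wholly on the assumed onset. This is a worthwhile, inexpensive improvement. It rests on the schedule as written and on the scheduled-values rule in Section 15.1.1, and it implies no change to the stopping criteria.

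**What to change.** 1. **Part B Day 8 call.** Ask every volunteer the Appendix 1 items that she can report: pain on the 1–10 scale, itching, and the size of redness, bruising and swelling. Record each as the worst since the dose, with start and stop dates.
2. **Existing assessments up to Day 85.** Beside the current grade, record the worst reaction since the last contact. Report the maximum per dose next to the by-visit table, with staff-graded and volunteer-reported values kept separate. Enter the new items in the Schedules of Assessments so that they count as scheduled values under Section 15.1.1.
3. **Preferably, a short solicited-reaction card** for Days 1–7 after each dose. Item 1 reaches only Part B dose 1, and item 2 relies on two-week recall after the boosters, so the card closes the gap best.

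Items 1 and 2 need a protocol amendment, a call script, some eCRF fields and one table, with no extra visit. The card costs more: it is a new use of a diary card in Part B and a new instrument in Part A. The downsides are some volunteer burden, recall error, and self-measured sizes that are less precise than staff measurement and cannot replace palpation for grade 1 induration.
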